 - History of abdominal fistula, gastrointestinal perforation, or intra-abdominal abscess ≤ 28 days prior to registration.
 - Clinically significant gastrointestinal abnormalities that may affect absorption of investigational product including, but not limited to:
 - Malabsorption syndrome
 - Major resection of the stomach or small bowel.
- 3.29c Corrected QT interval (QTc) > 480 msec using Bazett's formula.
- 3.29d Receiving any medications or substances with risk of torsades de pointes (see Appendix II). Note: medications or substances on the list "Drugs with Risk of Torsades de Pointes" are prohibited. Medications or substances on the list "Drugs with Possible or Conditional Risk of Torsades de Pointes" may be used while on study with extreme caution and careful monitoring.
- 3.29e Known endobronchial lesions and/or lesions infiltrating major pulmonary vessels and/or hemoptysis in excess of 2.5 mL (or one half teaspoon) ≤ 8 weeks of registration
- 3.29f Treatment with any of the following anti-cancer therapies: radiation therapy, surgery or tumor embolization, chemotherapy, immunotherapy, biologic therapy, investigational therapy or hormonal therapy ≤ 14 days prior to registration.
- 3.39g Prior autologous or allogeneic organ or tissue transplantation.
- 3.39h Elective or planned major surgery to be performed during the course of

the trial.

- 3.39i Receiving any medications or substances that are **strong or moderate inhibitors** of CYP3A4 (for a listing of medications or substances see Appendix VI).

Use of the following strong or moderate inhibitors are prohibited ≤ 7 days prior to registration.

- 3.39j Receiving any medications or substances that are **inducers** of CYP3A4 (for a listing of medications or substances see Appendix VI).

Use of inducers are prohibited ≤ 7 days prior to registration.

4.0 Test Schedule	Active Monitoring Phase					
	≤28 days prior to registration	≤14 days prior to registration	Day 1 ⁴ , Every cycle	On interval weeks 2, 6, 10	Every other cycle	End of treatment
Tests and procedures						
Informed Consent	X					
History and exam, Wt, PS			X			X
Adverse event assessment			X			
Height		X				
Pregnancy test		X ²				
Vital Signs, including temperature		X	X			X
Echo (2D M-Mode)	X ^R				X ⁸	
Hematology CBC with diff, platelets		X	X ^{R,6}			X
Chemistries ¹		X	X ^{R,6}	X ⁹		X
UPC Urine		X				
Thyroid Function Test (TSH)		X ^R			X ^R	
Coagulation Test: PT, PTT		X	X			
CT Head/MRI		X ^R				

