CT scan of chest, abdomen or pelvis, MRI, etc		X ^R			X ⁷	
Bone Scan					X ⁵	
EKG		X ^R	X			
Medication Diary			X ³			

1. SGOT, SGPT, total bili, Na, K, Cl, CO₂, BUN, creatinine, LDH, hemoglobin, calcium, albumin, total protein, magnesium, phosphorus and alkaline phosphatase.
2. For women of childbearing potential, ≤7 days prior to registration.
3. The diary must begin the day the patient starts taking the medication and must be completed per protocol and returned to the treating institution OR compliance must be documented in the medical record by any member of the care team.
4. +/- 3 days
5. If applicable
6. Research funded, cycles 1 and 2 only
7. Use the same method throughout the study. Follow-up scans to be performed every other cycle (8 weeks). Repeat measurements are required 8 weeks following an objective Response. See Section 11.0 for full RECIST criteria.
8. Every 4 months while on study, sooner should clinical symptoms indicate. These follow-up echocardiograms will coincide with restaging visits.
9. SGOT, SGPT, total bili, only and can be done at study site or locally and faxed.
- R Research funded (see Section 19.0)

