7.12 Dosage and Administration

Administration of pazopanib with a high-fat or low-fat meal results in an approximately 2-fold increase in area under the plasma drug concentration curve (AUC) and maximum observed plasma drug concentration (C_{max}).

Pazopanib should be taken orally without food at least one hour before or two hours after a meal. The tablets should be swallowed whole and must not be crushed or broken. The time of day the tablets are taken should be relatively constant.

If a dose is missed, the subject should take the dose as soon as possible, but only if there are 12 or more hours remaining before the next dose is due. If the next dose is due in less than 12 hours, the subject should skip the missed dose and take the next dose as scheduled.

If vomiting occurs after taking pazopanib, the subject should not take a replacement dose on that day. The subject should resume taking pazopanib at the next scheduled dose on the following day. If vomiting persists, the subject should be instructed to notify the investigator.

As a general rule, if dose reduction of pazopanib is necessary, the dose should be reduced stepwise by 200 mg at each step, and the subject should be monitored for approximately 10 to 14 days at each dose level. If toxicity does not abate during this monitoring time, the medication may need to be interrupted and/or the dose further decreased with continued monitoring for an additional 10-14 days at each dose level, and so on.

If the toxicity has abated with reduction of the dose and dose re-escalation is considered safe by the investigator, the dose can then be increased step-wise back to the pre-event dose (in 200 mg increments, after monitoring for 10-14 days at each dose level to ensure that toxicity did not recur or worsen).

If a subject's treatment has been interrupted for more than 21 days, the Investigator must contact the Study Physician to review the subject's condition in order to resume the treatment.

- 7.2 Patients can be instructed in administration techniques and granted treatment independence with nursing staff approval.
- 7.3 For this protocol, the patient must return to Mayo Rochester, Florida, or Arizona for evaluation at least every 28 days (+/- 3 days).

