8.3 Dose Modification Algorithms for Potential Treatment-Related Adverse Events

AE Terms & Descriptions	Dose Modification Algorithms
Hypertension	
Scenario A) 
 • Asymptomatic and persistent^d SBP of ≥140 and <160 mmHg, or DBP ≥90 and <100 mmHg, or 
 • Clinically significant increase in DBP of 20 mmHg (but still below 110 mmHg). 	
 • Continue pazopanib treatment at the current dose • Adjust current or initiate new antihypertensive medication • Titrate antihypertensive medication(s) during the next 2 weeks as indicated to achieve well-controlled^b BP • If BP is not well controlled within 2 weeks, consider referral to a specialist and go to scenario (B).
(Scenario B) 
 • Asymptomatic SBP ≥160 mmHg, or DBP ≥100 mmHg, or 
 • Failure to achieve well-controlled BP within 2 weeks in Scenario A 	
 • Interrupt pazopanib treatment if clinically indicated • Adjust current or initiate new antihypertensive medication(s) • Titrate antihypertensive medication(s) during the next 2 weeks as indicated to achieve well-controlled BP • Once BP is well controlled^e, restart pazopanib treatment reduced by one dose level
or 
 • Symptomatic^f hypertension or 
 • Persistent^g SBP ≥160 mmHg, or DBP ≥100 mmHg, despite antihypertensive medication and dose reduction of study treatment 	
 • Interrupt pazopanib treatment • Adjust current or initiate new antihypertensive medication(s) • Titrate antihypertensive medication during the next 2 weeks as indicated to achieve well-controlled BP • Referral to a specialist for further evaluation and follow-up is recommended • Once BP is well controlled, restart pazopanib treatment reduced by one dose level

Refractory hypertension unresponsive to above interventions.	
 • Permanently discontinue pazopanib treatment • Continue follow-up per protocol.
LVEF-drop (%) or CTCAE grade	Action and Dose Modification

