SAEs brought to the attention of the investigator at any time after cessation of pazopanib and considered by the investigator to be related or possibly related to pazopanib must be reported to Novartis if and when they occur. Additionally, in order to fulfill international reporting obligations, SAEs that are related to study participation (e.g., procedures, invasive tests, change from existing therapy) or are related to a concurrent medication will be collected and recorded from the time the subject consents to participate in the study until he/she is discharged.

- 10.6 Adverse events to be graded at each evaluation and pretreatment symptoms/conditions to be evaluated at baseline per the CTCAE v4.0 grading unless otherwise stated in the table below:

System Organ Class (SOC)	Adverse event/Symptoms	Baseline	Each evaluation
Gastrointestinal Disorders	Baseline number of stools per day	X	
	Diarrhea		X
Vascular Disorders	Hypertension	X	X
General disorders and administration site conditions	Fatigue	X	X
Investigations	Alanine aminotransferase increased	X	X
	Aspartate aminotransferase increased	X	X
	Blood bilirubin increased	X	X
	Lymphocytes decreased	X	X
Metabolism and Nutrition Disorders	Hypophosphatemia	X	X
	Hyponatremia	X	X
	Hypomagnesemia	X	X

10.61 Submit via appropriate MCCC Case Report Forms (i.e., paper or electronic, as applicable) the following AEs experienced by a patient and not specified in Section 10.6.

10.611 Grade 2 AEs deemed *possibly, probably, or definitely* related to the study treatment or procedure.

10.612 Grade 3 and 4 AEs regardless of attribution to the study treatment or procedure.

10.613 Grade 5 AEs (Deaths)

10.6131 Any death within 30 days of the patient's last study treatment or procedure regardless of attribution to the study treatment or procedure.

10.6132 Any death more than 30 days after the patient's last study treatment or procedure that is felt to be at least possibly treatment related must also be submitted as a Grade 5 AE, with a CTCAE type and attribution assigned.

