Vascular: Cerebral hemorrhage, hematuria

Gastrointestinal: Gastrointestinal fistula

Hepatobiliary: Hyperbilirubinemia

Skin and subcutaneous tissue: Rash

Renal and urinary: Proteinuria

General: Asthenia

Laboratory Abnormalities: $\geq 15\%$:

Leukopenia, neutropenia, thrombocytopenia, lymphocytopenia, anemia, ALKP increased, ALT increased, AST increased, albumin decreased, glucose increased, total bilirubin increased, sodium decreased, potassium increased.

Post Marketing Adverse Drug Reactions

Very common: $\geq 1/10$ ($\geq 10\%$)

Musculoskeletal and connective tissue: Arthralgia

Common: $\geq 1/100$ and $< 1/10$ ($\geq 1\%$ and $< 10\%$)

Infections and infestations (with or without neutropenia)

Gastrointestinal: Flatulence

Hepatobiliary: Gamma-glutamyl transpeptidase increased

Musculoskeletal and connective tissue: Muscle spasms

Uncommon: $\geq 1/1,000$ and $< 1/100$ ($\geq 0.1\%$ and $< 1\%$)

Blood and lymphatic system: Thrombotic microangiopathy (including thrombotic thrombocytopenic purpura and hemolytic uremic syndrome), polycythemia

Eye: Retinal detachment/tear

Gastrointestinal: Pancreatitis

Rare: $\geq 1/10,000$ and $< 1/1,000$ ($\geq 0.01\%$ and $< 0.1\%$)

Nervous system: Posterior reversible encephalopathy syndrome

Respiratory, thoracic and mediastinal: Interstitial lung disease/pneumonitis

- 15.18 **Drug procurement:** Pazopanib HCl (GW786034) is an investigational agent that will be supplied by Novartis. See Appendix V for detailed drug ordering instructions/form.
- 15.2 Nursing Guidelines for pazopanib
- 15.21 Pazopanib should be taken without food (1 hour before or 2 hours after a meal). Should be taken whole with water and not broken or crushed. If a dose is missed, do not take if it is less than 12 hours until the next dose.
- 15.22 There are numerous drug to drug interactions between pazopanib and other agents metabolized through the P450 system. Assess patient's concomitant medications, including OTC and herbal products. Refer to appendix for medications that should be avoided or used concomitantly with caution.
- 15.23 Hypertension is the most commonly reported side effect. Monitor blood pressure closely per study guidelines. Administer antihypertensives as ordered by MD.
- 15.24 Inform patient of possible changes in hair color.
- 15.25 Gastrointestinal side effects are common (diarrhea, nausea, vomiting, loss of appetite). Treat symptomatically and assess for effectiveness.

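### Section 4.0 schedules no blood pressure reading between Day 1 visits, so hypertension that first arises in Cycle 1 need not be measured until Cycle 2 Day 1

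*Combined protocol and SAP*

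**What the plan says.** The row "Vital Signs, including temperature" in the section 4.0 table is marked at screening (within 14 days before registration), on Day 1 of every cycle and at end of treatment. It is blank in the column for weeks 2, 6 and 10. In that column only Chemistries is marked, and footnote 9 restricts it: "SGOT, SGPT, total bili, only and can be done at study site or locally and faxed". History and exam, and adverse event assessment, are blank there too.

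Other text that bears on blood pressure:

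- Section 7.3 requires a return visit at least every 28 days, give or take 3 days. Footnote 4 of section 4.0 gives Day 1 the same window.
- Section 15.23 (nursing guidelines): "Hypertension is the most commonly reported side effect. Monitor blood pressure closely per study guidelines".
- Section 10.6 lists hypertension under "Adverse events to be graded at each evaluation and pretreatment symptoms/conditions to be evaluated at baseline".
- Section 7.12, after a dose reduction: "the subject should be monitored for approximately 10 to 14 days at each dose level".
- Section 8.3, once hypertension has been found: "Titrate antihypertensive medication(s) during the next 2 weeks as indicated". Under Scenario A, failure to reach control within 2 weeks moves the patient to Scenario B.
- Section 1.5 says that the protocol is meant to watch the class effects of VEGF inhibitors closely.

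**The concern.** The protocol names hypertension as an expected and frequent effect of the drug and has a detailed algorithm for it in section 8.3. That algorithm starts only when a raised reading has been taken. For a patient with normal pressure on Cycle 1 Day 1, the plan prescribes no further reading until the next Day 1 visit. Mid-cycle checks already exist for liver toxicity, but blood pressure was not added to them.

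What is at stake is patient safety during the first month of exposure: how soon new hypertension is seen and treated. There is also a small effect on the toxicity description (goal 2.23). Section 16.323 tabulates the maximum grade per patient, and a rise that came and went between visits might not be recorded.

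**Working it through.** The plan gives no figure for this interval. The check is a reading of the schedule followed by date arithmetic. Blood pressure is not named in section 4.0 and is taken to be part of vital signs.

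**1. Does any other text require a mid-cycle reading before hypertension has been found?**

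- 7.3 sets a minimum visit frequency and adds no mid-cycle visit.
- 15.23 asks for close monitoring but refers back to the study guidelines and gives no interval.
- 10.6 applies at each evaluation, and section 4.0 schedules no adverse event assessment at weeks 2, 6 or 10.
- 7.12 applies only after a dose reduction.
- 8.3 applies only after hypertension has been detected.

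None of them does.

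**2. Interval without a scheduled reading**

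- Nominal, Cycle 1 Day 1 to Cycle 2 Day 1: 28 days.
- With the section 7.3 window: 28 - 3 = 25 to 28 + 3 = 31 days.
- Between later Day 1 visits, if the windows are anchored to the calendar and both ends move: up to 28 + 3 + 3 = 34 days. If 7.3 is a rolling interval, the limit stays at 31.

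**3. Interval if weeks 2, 6 and 10 carried a reading**

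These weeks are days 14, 42 and 70, the midpoints of cycles 1, 2 and 3.

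- Nominal gap in those cycles: 28 / 2 = 14 days.
- Longest Cycle 1 gap, with the week 2 reading on day 14: 31 - 14 = 17 days.
- Treatment is capped at 12 months (7.4), which is 365 / 28 = 13.0 cycles. The remaining 13 - 3 = 10 cycles would keep the 28-day gap.

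**4. How common the event is (Appendix VII, VEG105192)**

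| | Pazopanib | Placebo |
|---|---|---|
| Any grade | 115/290 = 39.7% | 15/145 = 10.3% |
| Grade 3 | 13/290 = 4.5% | 1/145 = 0.7% |
| Grade 4 | 0 | 0 |

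Applied to the 39 patients to be accrued: 39 x 115/290 = 15.5 with any grade and 39 x 13/290 = 1.7 with grade 3. These are counts over the whole of treatment. They are not counts for Cycle 1.

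**5. Cost of the added readings**

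3 readings x 39 patients = 117 at most.

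**The case against.** The strongest case against the point has four parts.

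- **The re-check is already covered.** A reader might infer that the 2-week decision in Scenario A of section 8.3 has no reading behind it. The documents do not support that. A site cannot titrate to a blood pressure target and judge control within 2 weeks without measuring, so the instruction carries its own re-check. Its absence from section 4.0 fits the way the protocol is built: weekly urine protein, repeat echocardiograms, INR checks and weekly liver panels are also prescribed in section 8 and left out of 4.0. This part stands, and it confines the point to first detection.
- **No consequence is shown.** The documents hold no data on time to onset, so a reader who takes the 15.5 expected cases as patients missed in Cycle 1 goes too far. Grade 4 was absent in VEG105192. Diarrhea was more frequent there (150/290, 52%), so the ranking in 15.23 does not match that study. This stands as a limit on size.
- **Other safeguards exist.** Section 3.25 excludes patients with systolic pressure of 140 mmHg or more or diastolic of 90 or more. Sections 15.29 and 15.29a tell patients to report cardiac and neurological symptoms at once. Clinicians may take extra readings, and 15.23 encourages it. These reduce the risk, but none requires a reading in a patient without symptoms.
- **The week 2 contact may be no visit at all.** Footnote 9 allows a local blood draw with faxed results, so adding a reading is more than a mark in a table. This stands as a cost of the fix.

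**Conclusion.** The concern holds for first detection. As written, the plan allows hypertension that begins in Cycle 1 to go unmeasured for up to 28 days nominally (25 to 31 under 7.3), and for up to 34 days between later visits if the windows are anchored. That is looser than section 1.5 implies, for an event reported in about 40% of patients on pazopanib in VEG105192 against about 10% on placebo.

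The conclusion rests on two assumptions: that blood pressure is part of vital signs, and that a site does what the schedule requires and no more. The number of patients affected cannot be worked out from the documents. Severity is minor. The primary endpoint counts 12-month survivors and does not use blood pressure, so neither that analysis nor the sample size changes.

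**What to change.** Add a blood pressure reading to the week 2, 6 and 10 column of section 4.0. A footnote should allow it to be taken in clinic, locally or at home, and should require that it be sent to the site and reviewed there by a named role. Week 2 is proposed because the column already exists; the documents give no onset data that would single out that week.

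The cost is at most 117 readings over the trial. The main downside is practical: where the contact is only a local blood draw, the reading must be taken and sent separately, and someone at the site must be responsible for acting on it. The footnote should also say whether a local or home reading counts towards the visits by which section 8.3, footnotes d and e, define persistent and controlled hypertension.

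A line in section 8.3 that spells out the 2-week re-check would be an optional clarification of what that section already implies. It would also serve the later cycles, which have no week 2, 6 or 10 contact.

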5.0 Stratification / Grouping Factor: None.**6.0 Registration Procedures**

- 6.1 To register a patient, access the Mayo Clinic Cancer Center (MCCC) web page and enter the registration/randomization application. The registration/randomization application is available 24 hours a day, 7 days a week. Back up and/or system support contact information is available on the Web site. If unable to access the Web site, call the MCCC Registration Office at [contact] between the hours of 8 a.m. and 4:30 p.m. Central Time (Monday through Friday).

The instructions for the registration/randomization application are available on the MCCC web page [REDACTED] and detail the process for completing and confirming patient registration. Prior to initiation of protocol treatment, this process must be completed in its entirety and a MCCC subject ID number must be available as noted in the instructions. It is the responsibility of the individual registering the patient to confirm the process has been successfully completed prior to release of the study agent. Patient registration via the registration/randomization application can be confirmed in any of the following ways:

- Contact the MCCC Registration Office [REDACTED]. If the patient was fully registered, the MCCC Registration Office staff can access the information from the centralized database and confirm the registration.
- Refer to “Instructions for Remote Registration” in section “Finding/Displaying Information about A Registered Subject.”

- 6.2 Documentation of IRB approval must be on file in the Registration Office before an investigator may register any patients.

In addition to submitting initial IRB approval documents, ongoing IRB approval documentation must be on file (no less than annually) at the Registration Office [REDACTED]. If the necessary documentation is not submitted in advance of attempting patient registration, the registration will not be accepted and the patient may not be enrolled in the protocol until the situation is resolved.

When the study has been permanently closed to patient enrollment, submission of annual IRB approvals to the Registration Office is no longer necessary.

- 6.3 Prior to accepting the registration, registration application will verify the following:
- IRB approval at the registering institution
 - Patient eligibility
 - Existence of a signed consent form
 - Existence of a signed authorization for use and disclosure of protected health information
- 6.4 At the time of registration, the following will be recorded:
- Patient has/has not given permission to store and use his/her sample(s) for unspecified future research of renal cancer at Mayo.
 - Patient has/has not given permission to store and use his/her sample(s) for future

- research to learn, prevent, or treat other health problems.
- Patient has/has not given permission for MCCC to give his/her sample(s) to researchers at other institutions.
- Patient has given permission to store and use his/her samples for the mandatory future banking(section 14.1)

- 6.5 Treatment cannot begin prior to registration and must begin \leq 14 days after registration.
- 6.6 Pretreatment tests/procedures (see Section 4.0) must be completed within the guidelines specified on the test schedule.
- 6.7 All required baseline symptoms (see Section 10.3) must be documented and graded.
- 6.8 Treatment on this protocol must commence at Mayo Clinic Rochester, Mayo Clinic Arizona, or Mayo Clinic Florida under the supervision of a medical oncologist who confirms the patient is a suitable candidate for this study.
- 6.9a Study drug is available on site.

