13.0 Treatment/Follow-up Decision at Evaluation of Patient

- 13.1 Patients who are CR, PR, or SD will continue treatment per protocol.
- 13.2 Patients who develop PD while receiving therapy will go to the event-monitoring phase.
- 13.3 Patients who go off protocol treatment for reasons other than PD will go to the event-monitoring phase per Section 18.0.
- 13.4 Patients who develop non-CNS PD at any time should go to event monitoring.
- 13.5 A patient is deemed *ineligible* if after registration, it is determined that at the time of registration, the patient did not satisfy each and every eligibility criteria for study entry. The patient may continue treatment off-protocol at the discretion of the physician as long as there are no safety concerns, and the patient was properly registered. The patient will go directly to the event-monitoring phase of the study (or off study, if applicable).
- If the patient received treatment, all data up until the point of confirmation of ineligibility must be submitted. Event monitoring will be required per Section 18.0 of the protocol.
 - If the patient never received treatment, on-study material must be submitted. Event monitoring will be required per Section 18.0 of the protocol.
- 13.6 A patient is deemed a *major violation*, if protocol requirements regarding treatment in cycle 1 of the initial therapy are severely violated that evaluability for primary end point is questionable. All data up until the point of confirmation of a major violation must be submitted. The patient will go directly to the event-monitoring phase of the study. The patient may continue treatment off-protocol at the discretion of the physician as long as there are no safety concerns, and the patient was properly registered. Event monitoring will be required per Section 18.0 of the protocol.

- 13.7 A patient is deemed a cancel if he/she is removed from the study for any reason before any study treatment is given. On-study material and the End of Active Treatment/Cancel Notification Form must be submitted. The patient will go directly to the event-monitoring phase of the study, and event monitoring will be required per Section 18.0 of the protocol.

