16.0 Statistical Considerations and Methodology

- 16.1 Overview: This protocol will assess the efficacy of pazopanib in patients with non-clear cell metastatic renal cancer using a one-stage phase II study design.
- 16.11 Primary Endpoint: The primary endpoint of this trial is the 12-month overall survival rate. A “12-month overall survivor” will be considered synonymous with “success”, unless otherwise specified. A patient is considered to be a 12-month survivor if the patient lives 12 months from registration (note, all deaths prior to 12 months, regardless of cause, will be considered a failure). All patients meeting the eligibility criteria who have signed a consent form and have begun treatment will be evaluable for the primary endpoint. All eligible patients will be followed until death or a minimum of 2 years.
- 16.2 Statistical Design:
- 16.21 Decision Rule: The largest success proportion where the proposed treatment regimen would be considered ineffective in this population is 55%, and the smallest success proportion that would warrant subsequent studies with the proposed regimen in this patient population is 75%. The one-stage design based on properties of the binomial distribution uses 39 patients to test the null hypothesis that the true success proportion in a given patient population is at most 55%.
- 16.22 Sample Size: There will be 35 evaluable patients accrued onto this study unless undue toxicity is encountered. We anticipate accruing an additional 4 patients to account for ineligibility, cancellation, major treatment violation, or other reasons.
- 16.23 Accrual Time and Study Duration: The anticipated accrual rate is approximately 1-2 patients per month, based on the incidence of tumor type and the potential to accrue at Mayo Clinic sites (Mayo Clinic Rochester, Mayo Clinic Florida and Mayo Clinic Arizona). Therefore, the accrual period for this phase II study is expected to be 24 months. The final analysis can begin approximately 36 months after the trial begins, i.e. as soon as the last patient has been observed for 12 months.

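### The 12-month survival clock (16.11) starts at registration but only treated patients count, which gives a small upward bias, at most about 1.3 points under a constant hazard

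*Combined protocol and SAP*

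**What the plan says.** The time origin and the counting rule stand together in 16.11:

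- **Clock.** "A patient is considered to be a 12-month survivor if the patient lives 12 months from registration".
- **Denominator.** "All patients meeting the eligibility criteria who have signed a consent form and have begun treatment will be evaluable for the primary endpoint". Section 16.311 repeats this, and 16.312 estimates the rate as successes over evaluable patients.
- **Gap.** Section 6.5: "Treatment cannot begin prior to registration and must begin" at most "14 days after registration". The gap therefore lies between 0 and 14 days and is never negative.
- **Exit before dosing.** Section 13.7: "A patient is deemed a cancel if he/she is removed from the study for any reason before any study treatment is given". Such patients go to event monitoring. Section 16.22 covers them in the accrual allowance: "We anticipate accruing an additional 4 patients to account for ineligibility, cancellation, major treatment violation, or other reasons".

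Section 16.11 also classes every death before 12 months as a failure. Section 16.322 times PFS from registration as well, without naming its analysis set. The plan contains no analysis of all registered patients and none timed from first dose.

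**The concern.** Time zero comes before the event that makes a patient countable. Each evaluable patient has, by definition, survived from registration to first dose, and that guaranteed time counts toward the 12 months. A patient who dies in the gap is not evaluable, so the death is lost from both numerator and denominator. The same holds for a patient who deteriorates, is withdrawn before dosing and dies later in the year.

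The trial has no control arm in which the effect could cancel. The comparator is a fixed 55% (16.24). According to 1.4 it comes from a Kaplan-Meier estimate running from distant metastases, with no stated condition of surviving to a first dose. An ineffective drug would thus show slightly more than 55%, and the true type I error would sit slightly above the binomial figure.

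**Working it through.** **Inputs.** Null 55%, alternative 75%, alpha at most 0.10, power 80% and 35 evaluable patients (16.21, 16.22, 16.24); total accrual 39 (16.22, 16.63); gap 0 to 14 days (6.5). The plan prints neither a success cut-off nor the sidedness of alpha. The cut-offs below are inferred.

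**The plan's own sample size.** n = [z(1−a)·√(0.55·0.45) + z(0.80)·√(0.75·0.25)]² / 0.20².

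- With a = 0.05 per side (two-sided 0.10), n = 34.97, so 35, which matches the plan.
- With one-sided a = 0.10, n = 25.1.
- In exact binomial terms, 35 patients with at least 24 successes have one-sided alpha 0.0729 and power 0.858. At least 23 successes would give 0.134, so 24 is the smallest cut-off that meets 0.10.
- On the two-sided reading the cut-off is 25, with upper-tail alpha 0.0354.

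**Effect of the gap.** Assume a constant hazard that gives 55% at 12 months. Survival to day d is S(d) = 0.55^(d/365.25). The null 12-month rate among patients alive at first dose is 0.55/S(d). For d = 14, S = 0.9773 and 0.55/0.9773 = 0.5627. Gap deaths expected in 39 registered patients are 39·(1 − S). Alpha is the exact binomial upper tail at the shifted rate.

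| Gap for every patient | S(d) | Gap deaths in 39 | Null rate, treated | Alpha, ≥24/35 | Alpha, ≥25/35 | Alpha, ≥26/39 |
|---|---|---|---|---|---|---|
| 0 days | 1 | 0 | 55.0% | 0.0729 | 0.0354 | 0.0952 |
| 3 days | 0.9951 | 0.19 | 55.3% | 0.0775 | 0.0380 | 0.1011 |
| 7 days | 0.9886 | 0.44 | 55.6% | 0.0839 | 0.0416 | 0.1093 |
| 14 days | 0.9773 | 0.88 | 56.3% | 0.0962 | 0.0488 | 0.1251 |

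Delays spread evenly over 0 to 14 days give almost the same result as 7 days for everyone: 55.6%, and alpha 0.0839 at 24/35.

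**Sensitivity to the hazard in the gap** (14 days for all, ≥24/35). At 0.25, 0.5, 2 and 3 times the average hazard, alpha is 0.078, 0.084, 0.125 and 0.161. Alpha reaches 0.10 when the treated null rate is about 56.46%, so S = 0.55/0.5646 = 0.974, which is about 16 days at the average hazard. That corresponds to about 1.14 times average over 14 days (16/14), or about 2.3 times over 7 days (16/7).

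**Sensitivity to deteriorating cancels** (illustration). If 1 of 39 registered patients is cancelled and would have died within the year, the treated null rate is 0.55·39/38 = 56.4% and alpha at 24/35 is 0.0998. With 2 such patients it is 0.55·39/37 = 58.0% and 0.135.

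**The case against.** The strongest reply is that nothing fails on the powered design. Even when every patient waits the full 14 days, alpha at the average hazard is 0.096 against 0.10 (cut-off 24), or 0.049 against 0.05 (cut-off 25). This stands.

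A reader might infer from the last column of the table that the test breaches 0.10. The documents do not support that. Section 16.21 does speak of 39 patients, but 16.22 and 16.24 set 35 evaluable plus 4 for attrition, and the accrual table in 16.63 totals 39. The bias arises because some registered patients are dropped, so 39 registered cannot also be 39 evaluable. With one dropped, 38 patients and a cut-off of 26 give 0.088 at 14 days. With two dropped, 37 and a cut-off of 25 give 0.111, so the excess comes and goes with binomial discreteness. The 35-versus-39 conflict is a separate matter.

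A reader might also infer that the final estimate must be too high. That is not shown either. Section 16.311 scores patients lost before 12 months as failures, which pushes the estimate down, and one such patient in 35 is 2.9 points. It is a different rule and cannot be relied on to offset this one, but it leaves the net direction open.

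Nor does 16.11 contradict itself. Its statement on deaths can be read as classifying outcomes within the evaluable set, which is openly defined.

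Three further points limit the size:

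- Entry criteria (ECOG 0 to 2, laboratory limits, no severe comorbidity) should lower 14-day mortality.
- Section 6.9a says the drug is on site, so supply gives no reason for long waits.
- The benchmark is coarse: 55.2% from 74 registry cases has a simple binomial standard error of √(0.552·0.448/74) = 5.8 points. It runs from distant metastases, whereas 3.13 allows one prior treatment for metastatic disease. Moving the clock by up to 14 days does not align it with that origin.

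Against this, 3.12 admits collecting duct and medullary histology, which 1.1 describes as very aggressive. An early hazard above average therefore cannot be ruled out.

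**Conclusion.** The mismatch between clock and denominator is in the text, and by itself it can only favour the drug. It is minor: about +0.6 points for a 7-day gap and +1.3 points if everyone waits 14 days. With 35 evaluable patients and at least 24 successes, alpha rises from 0.073 to 0.084 or 0.096 and stays within 0.10.

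Alpha passes 0.10 only if 39 evaluable patients are tested, or if the pre-dose hazard or the number of poor-prognosis cancels is above what the null implies. At the 14-day bound a modest excess is enough; at a 7-day gap the hazard would have to more than double.

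These figures rest on a constant hazard at the null, inferred cut-offs and assumed delays. The documents give neither actual waiting times nor early mortality. The point is worth acting on because the correction is cheap, not because the design fails.

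**What to change.** Amend 16.11 in one of two ways:

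1. Time the primary endpoint, and PFS, from the first pazopanib dose, the moment at which a patient becomes evaluable. Under a constant hazard this restores the null rate to 55%. Sections 16.311 and 16.322, the completion-date definition in 16.5 and the 2-year follow-up limit in 18.1 then need to be aligned.
2. Keep the registration clock as it is.

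In either case add one sensitivity tabulation: 12-month survival from registration in all eligible registered patients, with deaths before first dose counted as failures. This also captures patients who deteriorate and are cancelled, which a first-dose clock alone does not. It should state how a cancel without known 12-month status is classed. Section 13.7 already requires event monitoring of cancels, so no new data collection is needed.

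The cost is a few consistency edits and one extra table. With the first-dose clock, the final analysis may come up to 14 days later. The estimate may be about 1 point lower.
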